2.	Gender DOB: Race (Check all that apply):
	White or Caucasian Black or African American Asian Native Hawaiian or other Pacific Islander American Indian or Alaska Native Other (specify)
4.	Ethnicity:
	Hispanic Non-Hispanic
5.	Highest Level of Education
	Some high school or less High school graduate or GED Some college, no degree Associate's degree Bachelor's degree Graduate degree

Nicotine Use History Questionnaire

1.	Average number of cigaret	tes smoked per day during the past 3 months?
	a. What brand do you	smoke?
	b. What size (mm)	(70, 72,84, 100,120, other: specify, not applicable)
	c. Menthol or tobacco	flavor?
	i.Full flavor Me	edium Light Ultralight
	iii.Filter Non filter	
		 roll your own
2.	Age started smoking?	
3.	Maximum CPD smoked on	average during any one year since started smoking?
4.	Number of serious quit atte	· · · · · · · · · · · · · · · · · · ·
5.	If >0:	· ——
	a. Longest time quit si	moking? Years Months Days
	b. Methods used to qu	it smoking:
	i.Counseling	Yes No
	ii.Nicotine gum	Yes No
	iii.Nicotine lozenge	
	iv.Nicotine patch	Yes No
	v.Nicotine Inhaler	Yes No
	vi.Nicotine nasal spray	Yes No
	vii.Chantix	Yes No
	viii.Zyban	Yes No
	ix.Electronic Cigarette	
6.	How many other smokers i	n your household?
7.	Other tobacco products use	ed
	a. Ecigarettes/vape	Yes No
	b. Hookah	Yes No
	c. Cigars	Yes No
	d. Smokeless tobacco	Yes No
	e. Other (please specif	fv·)

REALM Questionnaire

List 1

RAPID ESTIMATE OF ADULT LITERACY IN MEDICINE (REALM)©

List 2

	Correc t	Not Corre ct		Correc t	Not Correc t		Correc t	Not Correc t
Fat			fatigue			allergic		
Flu			pelvic			menstrual		
Pill			jaundice			testicle		
Dose			infection			colitis		
Eye			exercise			emergency		
Stress			behavior			medication		
Smear			prescription			occupation		
Nerves			notify			sexually		
Germs			gallbladder			alcoholism		
Meals			calories			irritation		
disease			depression			constipation		
cancer			miscarriage			gonorrhea		
caffeine			pregnancy			inflammatory		
Attack			arthritis			diabetes		
Kidney			nutrition			hepatitis		
hormones			menopause			antibiotics		
Herpes			appendix			diagnosis		
seizure			abnormal			potassium		
Bowel			syphilis			anemia		
asthma			hemorrhoids			obesity		
Rectal			nausea			osteoporosis		
Incest			directed			impetigo		

List 3

Tr + 1.0	CCC
Total Score:	of 66 correct
i Chai Dechie.	OI OO COITCCL

Minnesota Nicotine Withdrawal Scale (MNWS)

MNWS

4. Do you smoke more during the first hours after waking than during the rest of the day?
a) Yes
b) No
5. Which cigarette would you be the most unwilling to give up?
a) First in the morning
b) Any of the others
6. Do you smoke even when you are very ill?
a) Yes
b) No

[Date]	
RE: VARENICLINE OTC TRIAL ON EFFICACY AND SAFETY	
Dear Doctor,	
Your patient, [First Name Last Name], has expressed interest in (NIH)-funded smoking cessation study entitled Varenicline OTC Site]. This study is designed to assess the safety and efficacy of or behavioral support.	Trial on Efficacy and Safety at our site [Name of
In order to participate in the study, a signed letter of permission may have the following condition:	n is required because the individual indicated they
☐ History depression	
Included with this form are study documents for your consideration whether they can participate in the study.	ation that might help you make a decision on
 -Copy of unsigned full Informed Consent (to be signed to participate in the entire study) -Chantix Medication Guide -Varenicline Use and Safety Information 	when/if subject has been approved [and is willing]
To be in this study, participants will receive use and safety inforconsent form in order to make a decision about whether or not approved criterion, they will be able to participate and use the documents are provided to you. If participants have questions to the study documents, or ask them to contact us at the numb questions for us, please use the contact information on the Cor	t participate. If they are elgible based on IRB- study product at their discretion. All of these about the study medication, please refer them back per provided in the Consent form. If you have
Please indicate your approval or disapproval below, and have y	our patient return the letter to us.
☐ I have reviewed the documents provided and approve my p above-noted study for the following reason(s):	
☐ I have reviewed the documents provided and do not appro in the above-noted study for the following reason(s):	
Physician Printed Name: Physician Address:	
Physician Signature:	Date:
Sincerely,	
[Printed Investigator First Name Last Name]	

Modified Cigarette Evaluation Questionnaire (mCEQ)*

If you have smoked since you last completed this questionnaire, please mark the number that best represents how smoking made you feel.

(1—not at	all, 2—very little, 3—a little, 4—moderately, 5—a lot, 6—quite a lot, 7—extremely).
1	_Was smoking satisfying?
2	Did cigarettes taste good?
3	_Did you enjoy the sensations in your throat and chest?
4	_Did smoking calm you down?
5	_Did smoking make you feel more awake?
6	_Did smoking make you feel less irritable?
7	Did smoking help you concentrate?
8	_Did smoking reduce your hunger for food?
9	_Did smoking make you dizzy?
10	_Did smoking make you nauseous?
11	_Did smoking immediately relieve your craving for a cigarette?
12	_Did you enjoy smoking?

Smoking Status and Resource Utilization

Smoking status

At al	l visits

- 1. Did you smoke any cigarettes, even a puff, since your last visit? Yes No
- 2. [If Yes to 1] Did you smoke any cigarettes, even a puff, in the last 7 days?

It has been approximately	weeks since your last visit.
3. On approximately how many days	s did you smoke?
4. On the days that you smoked, wh	at is the average number of cigarettes that you
smoked?	

Resource utilization

At all visits

- a. Since your last visit, which of the following additional things have you tried to reduce or quit smoking? Check all that apply.
- a) A pamphlet or book
- b) Individual or group counseling
- c) Telephone counseling / quitline
- d) Nicotine patch, gum, nasal spray, lozenge, or inhaler
- e) E-cigarettes
- f) Zyban / bupropion
- g) Switching to chewing tobacco or snuff
- h) Switching brands
- i) Cutting back
- j) An Internet quit smoking program
 k) Alternative methods like herbs, lasers, homeopathic medicines, prayer, acupuncture, or hypnosis

 Somet 	hing else:	
---------------------------	------------	--

Medication compliance and perceived efficacy

Medication	efficacy	and com	npliance

Λt	വ	\ / /	101	t-c
Αt	aı	ı v	ı	ເວ

- 5. This medication is helping me/has helped me quit smoking.
- a) Strongly disagree
- b) Somewhat disagree
- c) Neither agree nor disagree

d) Somewhat agree e) Strongly agree f) Don't know
At Week 2 telephone call only a. It has beendays since your last visit. After the first 3 days of taking the study medication the instructions were to take 2 pills per day. Approximately what percentage of days did you take: itwo doses per day iione dose per day iiino doses
At the Week 4, 8 and 12 visits 6. It has been number of days since your last visit.
Approximately what percentage of days did you take:two doses per dayone dose per dayno doses
Ask #7 only if any study product was reported as not used as recommended 7. Main reason for not using medication as recommended (check only one): forgotside effectnot workingdon't needother Specify:

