Visit Window. Table 2 shows the target and allowed windows for study visits. Except for Week 2 where the telephone visit should be no more than 2 days on either side of the target visit day, the allowed window for each visit is 5 days before or after the target visit. Visits outside of those ranges are allowed, but must be documented (eg vacation, difficulty contacting, illness, etc).

Table 2. Target and allowed windows for study visits for the In-person and remote cohorts.

Visit Week	Target Day in Relation to Randomization Date	Allowed Window (days)
BL		
2 (call)	14	12-16
4	28	23-33
8	52	47-57
12	98	93-103
13 (call)	105	100-110
26	182	177-187

Inclusion Criteria for the In-person Cohort

- 1. 21 years of age or older
- 2. Self-reported daily smoker
- 3. Breath CO > 10ppm
- 4. Motivated to quit smoking completely within five weeks of the Screening Visit (>5 on reported motivation)
- 5. Capable of and agree to complete study requirements
- 6. Literate in English, self-report

- 7. Must be available for the duration of study
- 8. Informed consent obtained
- 9. Willing and able to provide additional data between visits using ecological momentary assessment (EMA)
- 10. Must own study compatible smart-phone (iPhone or Android)

Exclusion Criteria for the In-person Cohort

- 1. Any self-report, diagnosis or treatment of heart attack, unstable angina, angioedema, seizures, cerebrovascular accident (CVA) within the last six months.
- 2. Any self-report, diagnosis or treatment of bipolar, schizophrenia or suicidal ideation within the last six months. (For suicidal ideation a score of ≥7 on the Suicidal Behavior Questionnaire, see Appendix 15)
- 3. Self-report of diagnosis or treatment for depression within the past six months, unless participant has written permission by their healthcare provider to participate
- 4. Systolic blood pressure 160 or higher and/or diastolic blood pressure 100 or higher (see site applicable SOP for Evaluating and Reporting Blood Pressure and Appendices 5 and 6 for participant handouts)
- 5. History of renal disease
- 6. Allergy to any of the ingredients in varenicline
- 7. Participation in another smoking cessation program or any type of clinical trial in the past 3 months
- 8. Use of any smoking cessation medication in the past three months
- 9. Any other medical condition(s) which the licensed study physician deems unacceptable for participation in this study

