participants no more than 90 seconds to complete. To reduce missing data, participants who miss more than two sequential days of evening daily diaries or complete fewer than three scheduled prompts a day for two sequential days will receive encouragement texts and calls from an RA to troubleshoot any problems with the app and encourage compliance.

Definitions of Success

FDA Abstinence Criteria. As indicated earlier, in all studies that assess medications for smoking cessation, the FDA typically requires verification of 28 days of continuous abstinence, i.e.; not a single puff from a single cigarette. The FDA does not require the 'clock' to start at a consistent time point after study enrollment. Thus, in many studies the 'clock' on that 28 days begins two weeks after study medication has begun, while in other studies the 'clock' starts at a different time point. In the current study, we will follow the protocol used in the varenicline pivotal trials. ^{6,17-20} The primary study outcome in the proposed study will be continuous abstinence between weeks 8 and 12 after study medication has begun. Subjects who are randomized but who never obtain medication will be considered treatment failures and will be included in the denominator in the intent-to-treat analyses.

D. DATA SAFETY MONITORING PLAN

Participant Safety. This study includes the use of a medication, varenicline, that is FDA-approved, as well as the same medication at a lower dose than approved by the FDA, in order to assess whether smokers can choose and use the medication without a healthcare provider prescription. Given the existing data, the likelihood of participants experiencing a serious adverse event from the use of varenicline is very low. In fact, in one of the largest smoking cessation studies ever conducted, the adverse events related to varenicline were similar to those from the nicotine patch, which is already approved as an OTC medication.

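### The smoking-status form asks about smoking since the last visit and collects no dates, so visit timing, not the weeks 8–12 window, sets the period behind the primary outcome

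*Combined protocol and SAP*

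**What the plan says.** Definitions of Success (FDA Abstinence Criteria) states that the primary outcome "will be continuous abstinence between weeks 8 and 12 after study medication has begun". The same paragraph gives the regulatory background, that "the FDA typically requires verification of 28 days of continuous abstinence", with no puff permitted.

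The self-report source is the Smoking Status and Resource Utilization form (Appendix 9), used at every follow-up contact. It has four smoking items:

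1. "Did you smoke any cigarettes, even a puff, since your last visit", answered Yes or No.
2. After a Yes only: "Did you smoke any cigarettes, even a puff, in the last 7 days".
3. A count that begins "On approximately how many days".
4. Average cigarettes on smoking days.

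It also records the approximate number of weeks since the last visit. No item asks when any smoking took place.

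Table 2 (Visit Window) counts days from randomization: week 4 at day 28 (23–33), week 8 at day 52 (47–57), week 12 at day 98 (93–103). The text adds: "Visits outside of those ranges are allowed, but must be documented". For the remote cohort, Screening/Baseline Visit 2 bases the later visits on the medication start date.

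Product Education Information recommends a quit date on day 8, or up to 30 days after starting the product. The only failure rule in Definitions of Success covers people who are randomized but never obtain medication. Nothing visible says how to score a week 8 visit that is missed, early or late.

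**The concern.** The outcome is defined on a fixed window, but the form measures a variable one. The week 12 answer matches weeks 8–12 only if the previous visit fell when the window opened and the week 12 visit fell when it closed. Otherwise the answer covers extra days, or omits some, and the form cannot separate smoking inside the window from smoking outside it.

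The main exposure is to people who quit late but within the plan's own allowance. If they miss week 8, their earlier smoking falls inside the week 12 lookback.

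No other listed source fills the gap. The schedules for both cohorts list only this form for smoking status. EMA diaries cover two weeks in a subsample. Breath CO and urine cotinine are taken at visits and do not date smoking across a four-week span.

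**Working it through.** **Inputs.** Visit days and windows: Table 2. Outcome window: weeks 8–12, nominally days 8 × 7 = 56 to 12 × 7 = 84, a span of 28 days, taking medication start as day 0 and equal to randomization. That equality is an assumption, because the anchors differ between sections.

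**Lookback of the week 12 question** = week 12 day − day of the last attended visit.

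| Situation | On target | Range within windows |
|---|---|---|
| Week 8 attended | 98 − 52 = 46 | 93 − 57 = 36 to 103 − 47 = 56 |
| Week 8 missed, week 4 attended | 98 − 28 = 70 | 93 − 33 = 60 to 103 − 23 = 80 |

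On-target visits add 56 − 52 = 4 days before the nominal window and 98 − 84 = 14 after it: 4 + 28 + 14 = 46. A missed week 8 adds 56 − 28 = 28 days before and 14 after: 28 + 28 + 14 = 70. Neither case leaves any of days 56–84 uncovered.

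**Missed week 8.** Take a participant who quits on day 30 and stays abstinent. They smoked after the day 28 visit, so item 1 at week 12 is Yes. Item 2 is No, which clears about days 91–98 only. Item 3 gives a number of smoking days without saying when they fell. The same answers could come from someone who smoked on days 60 and 61. The form cannot tell a success from a failure. A No to item 1, by contrast, establishes self-reported abstinence over the whole 70 days.

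**Late week 8.** Each day after day 56 moves one day of the window out of the week 12 question. At day 57, the window limit, one day is lost. At day 70, which is 13 days beyond that limit, 70 − 56 = 14 days are lost, although the lookback to day 98 is still 28 days. The week 8 form covers the displaced days, and its item 2 covers the last 7, about days 63–70. Only about days 57–62 then stay undated. If the visit is on or before day 63, a No to item 2 clears every displaced day. A Yes to item 2 at a visit on days 57–62 straddles the opening of the window, so it is not decisive.

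**Size.** The documents give no frequencies, so both inputs are assumed. Share of true successes lost, f = P(week 8 missed) × P(smoked in weeks 4–8, given abstinent in weeks 8–12):

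- Low: 0.05 × 0.10 = 0.5%; 23% × (1 − 0.005) = 22.9%.
- High: 0.20 × 0.40 = 8%; 23% × (1 − 0.08) = 21.2%.

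**Effect on power.** The Sample Size section plans 23% vs 8%, α = 0.025 (taken as two-sided), 110 per group, power at least 80%. Using power = Φ{[(p₁ − p₀)√n − z√(2p̄(1 − p̄))] / √[p₁(1 − p₁) + p₀(1 − p₀)]}, where z = 2.241 and p̄ = 0.155, the result is Φ[(1.573 − 1.147)/0.501] = 80.3%, so the plan's figure is reproduced. Applying the same f to both arms:

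| f | Rates | Difference | Power, 110 per group | Power, 432/3 = 144 per group |
|---|---|---|---|---|
| 0 | 23.0% vs 8.0% | 15.0 points | 80.3% | 90.4% |
| 0.5% | 22.9% vs 8.0% | 14.9 points | 80.0% | 90.2% |
| 8% | 21.2% vs 7.4% | 13.8 points | 75.8% | 87.1% |

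**The case against.** The strongest reply is that the form holds more than item 1. It records the interval since the last visit, and item 2 dates the latest week. Out-of-window visits must be documented, so they can be found. An in-window week 8 visit leaves at most one nominal day outside the week 12 question. The loss is small even at the upper end of the assumed range. Missed week 8 visits followed by abstinence may be uncommon, because in-person participants collect medication then and questionnaires are done by telephone where possible. Some appendix pages are not available here, and the unseen Procedure Manual may contain a scoring rule.

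Most of this stands, and it limits the point. A reader might infer that any missed or late week 8 visit makes the primary outcome wrong in either direction. The documents do not support that. A missed or early visit lengthens the lookback and can only produce false failures. A false success needs a late visit and scoring that disregards a Yes on the week 8 form, and no section prescribes such scoring. Nor does each week of delay simply shorten a 28-day question by 7 days: Table 2's targets are 46 days apart.

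The reply does not resolve the Yes at week 12 after a missed week 8. Neither the interval, the 7-day item nor the count of smoking days places that smoking inside or outside the window.

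**Conclusion.** The point holds as a limited weakness in data collection for the primary endpoint. The period assessed is 46 days on target visits and 70 days if week 8 is missed, against a nominal 28. Some true successes can be scored as failures. Late week 8 visits are a secondary issue.

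Under assumed inputs the loss is 0.5–8% of true successes, which takes 23% to between 22.9% and 21.2%. The power cost is up to about 4.5 percentage points at 110 per group (80.3% to 75.8%) and 3.3 at 144 (90.4% to 87.1%). This assumes equal loss in each arm and counts missed week 8 visits only. No frequency can be put on false successes from late visits.

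If the outcome is meant as abstinence between the week 8 and week 12 visits, the item fits on-time visits by definition, but it then covers 46 days and the missed-visit problem remains. The conclusion rests on the visible text, whose appendix list names no other smoking-status form.

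**What to change.** First reconcile the weeks 8–12 definition with Table 2's day 52 and day 98. Settle the anchor as well: Table 2 counts from randomization, while the outcome and the remote visits count from medication start.

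Then amend Appendix 9:

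- **Week 12:** add an item tied to calendar dates, such as *Between [date the window opens] and [date it closes], did you smoke at all, even one puff?* If Yes, record the first and last smoking dates in that period.
- **Week 8:** add the date of the last cigarette.

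State in Definitions of Success that the outcome is scored from these dates plus the week 12 verification, whether or not week 8 was attended or on time. Keep the existing items.

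The date of the last cigarette alone, asked at week 12, would not be enough. Someone abstinent on days 56–84 who lapsed on day 90 would give day 90 at a day 98 visit and look like a failure, so the question must name the window.

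The cost is one or two extra questions, a sentence in the protocol and some recall error in dates, greatest for those who missed week 8.

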- 1. To assess the safety and efficacy of the current FDA-approved 1 mg b.i.d. varenicline for smoking cessation in comparison with placebo when used in a simulated OTC study with no behavioral support provided.
- 2. To assess the safety and efficacy of .5mg b.i.d. varenicline in comparison with 1mg b.i.d. varenicline and placebo when used in a simulated OTC study with no behavioral support provided.

Secondary Objectives

- 1. To evaluate whether subject specific characteristics (e.g. socioeconomic status, ethnicity, smoking history, etc.) moderate primary (safety and efficacy) and secondary (adherence) outcomes.
- 2. To evaluate medication use patterns to assess whether varenicline is being used as indicated on the label, and to determine if medication adherence mediates cessation outcomes between-subjects.

3. In a subsample of participants, to examine how medication adherence, withdrawal, and side effects (e.g. nausea and sleep disturbance) vary within-subjects and are associated with smoking status using EMA in the first two critical weeks of medication use.

[figure not shown]
Hypotheses

- 1. Quit rates in the 1 mg b.i.d. varenicline condition will be significantly higher than the placebo medication condition when provided as an OTC medication.
- 2. Quit rates in the .5 mg b.i.d. varenicline condition will be comparable to the 1mg b.i.d. varenicline condition, and will be significantly higher than the placebo medication condition, when provided as an OTC medication.
- 3. Side effects will show a dose response relationship, with effects lowest in the placebo group.

C. EXPERIMENTAL METHODS Study Design

The primary objective of this study is to assess the efficacy of two different doses of varenicline used in a simulated OTC intervention relative to placebo (total N = 432). The design is a three-group placebo-controlled, double blind, block randomized clinical trial (as indicated in the figure), where participants will be randomly assigned to one of three

conditions: (1) 1 mg b.i.d. varenicline for 12 weeks, which is the current FDA-approved dose, (2) 0.5 mg b.i.d. varenicline for 12 weeks, or (3) placebo.

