A time will be scheduled for a phone call or Zoom meeting, the study will be described in written format and orally by study staff, and participants will be asked to electronically sign the consent form. The following will occur during Screening/Baseline:

- Informed Consent (electronic)
- Subject Demographics (see Appendix 1)
- Smoking, tobacco, and cessation medication use history (see Appendix 2)
- Rapid Estimate of Adult Literacy in Medicine (REALM, see Appendix 3)
- Minnesota Nicotine Withdrawal Scale (MNWS, see Appendix 4). This brief staff or subject administered form will assess cigarette-related craving and withdrawal.
- Medical History—Pertinent medical history will be assessed and documented on the Medical History CRF by the study coordinator through a review of systems, allergies, and recent surgeries
- Previous and Concomitant Medications. Medications taken within the previous 30 days of the Screening/Baseline visit will be documented in the Concomitant Medication CRF
- Fagerström Test of Cigarette Dependence (FTCD, see Appendix 7). This 5 item subject completed questionnaire measures dependence on cigarettes.

- If the subject requires study approval from their own physician, the Investigational Product will be dispensed upon receipt of the signed authorization (Appendix 8)
- Suicidal Behavior Questionnaire (Appendix 15)

Screening/Baseline for the Remote Cohort – Visit 2

- Urine pregnancy test for all females. This will be mailed to the participant after they have completed Screening/Baseline Visit 1.
 - Urine cotinine test. This will be mailed to the participant after they have completed Screening/Baseline Visit 1.
 - If subject meets all inclusion and exclusion criterion, a study ID will be assigned and he/she will be randomized in a 1:1:1 fashion to 1.0 mg b.i.d. varenicline, .5mg b.i.d. varenicline, or placebo. Participants and study staff will be blinded to the assignment.
 - Investigational Product educational information will be provided to participants
 - The Investigational Product will be dispensed to be used for the full 12 weeks of treatment
- Participants will have 30 days from the start of their first screening visit to complete all the procedures and begin the medication
- Participants will be asked to contact study staff when they receive the study medication to inform staff when they will be starting the medication so they remaining visits can be based on the medication start date.

Week 2 Visit for the Remote Cohort

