- Minnesota Nicotine Withdrawal Scale
- Adverse Events
- Concomitant Medications
- Smoking Status and Resource Utilization Assessment (See Appendix 9) (Brief site administered questionnaires assessing smoking status, smoking cessation resources used since last study visit
- Medication Adherence, and Perceived Efficacy Assessment (see Appendix 10) (Brief site administered questionnaires assessing pills taken since last study visit, and perceived efficacy of the medication.
- Modified Cigarette Evaluation Questionnaire (mCEQ), see Appendix 11). This 15item staff or subject administered questionnaire assesses the degree to which smokers experience the reinforcing effects of smoking.

Week 4 Visit for Remote Cohort

- Minnesota Nicotine Withdrawal Scale
- Adverse Events
- Concomitant Medications
- Smoking Status, and Resource Utilization Assessment
- Medication adherence and Perceived Efficacy Assessment
- Modified Cigarette Evaluation Questionnaire (mCEQ)

Week 8 Visit for the Remote Cohort

- Urine cotinine test, if they report not smoking
- Minnesota Nicotine Withdrawal Scale
- Adverse Events
- Concomitant Medications

- Smoking Status, and Resource Utilization Assessment
- Medication adherence and Perceived Efficacy Assessment
- Modified Cigarette Evaluation Questionnaire (mCEQ)

Week 12 for the Remote Cohort

- Urine cotinine test, if they report not smoking
- Minnesota Nicotine Withdrawal Scale
- Adverse Events
- Concomitant Medications
- Smoking Status, and Resource Utilization Assessment
- Medication Adherence and Perceived Efficacy Assessment
- Assess medication use by asking the participants to mail back any unused study medication
- Modified Cigarette Evaluation Questionnaire (mCEQ)

Week 13 for the Remote Cohort

- Smoking Status, and Resource Utilization Assessment
- Adverse Events
- Minnesota Nicotine Withdrawal Scale
- Concomitant Medications including Chantix[™] or other smoking cessation aids

Week 26 for the Remote Cohort

- Telephone call
- Smoking Status and Resource Utilization Assessment
- Urine cotinine test, if they report not smoking

Visit Window for the Remote Cohort. Will be the same as shown in Table 2.

Inclusion Criteria for the Remote Cohort

- 1. 21 years of age or older
- 2. Self-reported daily smoker
- 3. Positive cotinine from urine sample
- 4. Motivated to quit smoking completely within five weeks of the Screening Visit (>5 on reported motivation)
- 5. Capable of and agree to complete study requirements

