- 6. Literate in English, self-report
- 7. Must be available for the duration of study
- 8. Informed consent obtained
- 10. Must own study compatible smart-phone (iPhone or Android)
- 11. Must be a current resident of the United States

Exclusion Criteria for the Remote Cohort

1. Any self-report, diagnosis or treatment of heart attack, unstable angina, angioedema, seizures, cerebrovascular accident (CVA) within the last six months.

- 2. Any self-report, diagnosis or treatment of bipolar, schizophrenia or suicidal ideation within the last six months. (For suicidal ideation a score of ≥7 on the Suicidal Behavior Questionnaire, see Appendix 15)
- 3. Self-report of diagnosis or treatment for depression within the past six months, unless participant has written permission by their healthcare provider to participate
- 4. History of renal disease
- 5. Allergy to any of the ingredients in varenicline
- 6. Participation in another smoking cessation program or any type of clinical trial in the past 3 months
- 7. Use of any smoking cessation medication in the past three months
- 8. Any other medical condition(s) which the licensed study physician deems unacceptable for participation in this study
- 9. Consume greater than 21 alcohol drinks per week.
- 10. No two members of the same household may participate in this study
- 11. No study staff or their immediate family may participate in the study
- 12. Females who are pregnant, breast feeding, or not currently using a medically approved form of birth control and unwilling to do so.

 Acceptable methods of birth control include abstinence, oral contraceptives, the contraceptive patch, the contraceptive ring, and condoms.

Behavioral Support

No behavioral support will be provided by the study team at any visit. At all follow-up visits post-randomization, they will not be given encouragement by study staff to quit smoking, nor be provided with any information or instruction about medication usage other than consent form and Chantix Use and Safety Information handout (see Appendix 12). We will assess at each visit whether subjects used any behavioral support available in the community.

Risk/Benefit Assessment

Risk Category. Greater than minimal risk

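### The Week 2 adherence item restates the pill instruction despite the no-instruction rule, and its since-last-visit interval makes the score ambiguous and not comparable between cohorts

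*Combined protocol and SAP*

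**What the plan says.** Under Behavioral Support, the protocol sets a rule for every follow-up visit after randomization. It begins "At all follow-up visits post-randomization, they will not be given encouragement by study staff to quit smoking" and goes on to say that participants will not "nor be provided with any information or instruction about medication usage other than consent form and Chantix Use and Safety Information handout".

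Secondary Objective 2 is "To evaluate medication use patterns to assess whether varenicline is being used as indicated on the label", and to test whether adherence mediates cessation.

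The Week 2 visit lists for both cohorts describe the adherence form as "Brief site administered questionnaires assessing pills taken since last study visit, and perceived efficacy of the medication". In Appendix 10, the Week 2 item gives the number of days since the last visit and then states: "After the first 3 days of taking the study medication the instructions were to take 2 pills per day". It continues with "Approximately what percentage of days did you take" two doses, one dose or no doses. The Week 4, 8 and 12 item asks for the same percentages without restating the instruction.

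For the remote cohort, randomization takes place at Baseline Visit 2 and product is posted afterwards (Product Packaging). Participants tell staff when they will start, "so they remaining visits can be based on the medication start date". Table 2, which is also applied to the remote cohort, counts target days from randomization.

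**The concern.** There are two separate problems in one form item.

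First, the trial simulates over-the-counter use by withholding instruction after randomization. A staff member who states the schedule immediately before asking whether it was followed gives a cue to the expected answer. The statement may also remind someone who had misread the handout. The first would affect the Week 2 answer and the second only use after the call.

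Second, the interval named in the item is not the interval on medication. For a remote participant the last visit before Week 2 is Baseline Visit 2, when no drug was in hand. There is no response for not having started, so days spent waiting for the parcel can be reported only as days with no dose.

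At stake is the description of label use under Secondary Objective 2, and any comparison of adherence between cohorts. The plan analyses the cohorts separately and may combine them if their outcomes look similar, so an artefact confined to one cohort could distort that judgement for adherence.

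**Working it through.** The plan gives no expected adherence figure and no rule for scoring the percentages, so there is no figure of its own to reproduce.

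**Texts side by side.** The rule covers all follow-up visits and exempts two documents, the consent form and the handout. The Week 2 item is delivered by staff at a follow-up visit and states the pill schedule. Read literally, the two conflict, even if the sentence only repeats what the handout says.

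**Inputs for the interval**
- Pill schedule (Medication Dosing): one pill a day on days 1–3, then two a day, with the same pill count in every arm.
- Week 2 target day 14, window 12–16 (Table 2).
- *d* = days from Baseline Visit 2 to first pill in the remote cohort. The documents do not give it. The only limit is 30 days from the first screening visit to starting medication. Values of 3, 7 and 14 are assumed here.
- In person, the first pill is assumed to be taken at baseline (*d* = 0).

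Consider a participant who takes every pill as scheduled. In 14 medication days this gives 3 one-pill days and 14 − 3 = 11 two-pill days.

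**Literal reading: denominator is days since the last visit**
- In person: two-dose 11/14 = 78.6%, one-dose 3/14 = 21.4%, no-dose 0%. Across the window, two-dose runs from 9/12 = 75% to 13/16 = 81%.
- Remote, call on day 14 of medication: two-dose 11/(14 + *d*), no-dose *d*/(14 + *d*).
- Remote, call on day 14 after randomization (Table 2): two-dose (11 − *d*)/14, not below 0; no-dose *d*/14, not above 1.

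| Assumed *d* | Start-date anchor: two-dose | no-dose | Randomization anchor: two-dose | no-dose |
|---|---|---|---|---|
| 3 | 11/17 = 64.7% | 3/17 = 17.6% | 8/14 = 57.1% | 3/14 = 21.4% |
| 7 | 11/21 = 52.4% | 7/21 = 33.3% | 4/14 = 28.6% | 7/14 = 50.0% |
| 14 | 11/28 = 39.3% | 14/28 = 50.0% | 0% | 14/14 = 100% |

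**Alternative reading: medication days after day 3 only.** With 14 medication days the score is 11/11 = 100% in either cohort.

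**Counting from first pill.** With 14 medication days, two-dose 11/14 = 78.6%, one-dose 21.4% and no-dose 0%, the same in both cohorts.

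With the start-date anchor and *d* = 7, the same perfect behaviour can therefore be recorded as 100%, 79% or 52%, depending on reading and cohort.

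**The case against.** The case on the other side has substance.

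- **The sentence probably adds nothing new.** The rule exempts the handout, and Product Education Information says the handout covers how to use the medication. The item refers back to instructions already given, to frame a recall question. The handout's dosing text is not in the material available, so this cannot be confirmed. What remains is that staff repeat it at a follow-up visit.
- **The sentence cannot change the two weeks it asks about.** It is spoken afterwards. Only the remaining 84 − 14 = 70 treatment days could be affected.
- **The interval has another reasonable reading.** The lead-in about the first three days on medication may limit the question to later medication days, which removes the cohort difference.
- **Start dates are reported.** Remote participants tell staff when they will begin, so waiting days can be identified at analysis.
- **Other measures exist.** The SAP allows pill count, and unused product is returned. This stands for adherence over the whole treatment period. It does not repair the remote Week 2 measure, because remote product comes back only at Week 12. The EMA diaries are planned for only 75 participants.
- **The two effects may pull in opposite directions.** Cueing would tend to raise reported adherence, while waiting days lower it. Nothing suggests that they cancel.

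A reader might infer that the script turns all 432 participants into a coached population and so distorts efficacy and side effects. The documents do not support this. Only those who complete the Week 2 call hear the sentence, no effect on later use is shown, and the wording is identical in all three arms.

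**Conclusion.** The point holds in two limited parts.

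1. The Week 2 item conflicts with the literal no-instruction rule, and the two texts must be reconciled. The wording may cue Week 2 answers and may affect later use. The size of either effect cannot be derived from the documents, and there is no reason to expect it to differ by arm.
2. The item does not define one adherence measure. On the literal reading, with remote visits timed from medication start, a fully adherent remote participant scores 65%, 52% or 39% two-dose days at assumed lags of 3, 7 or 14 days, against 79% in person. On the other reading both score 100%. The measure is thus ambiguous and, as written, not comparable between cohorts.

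It would be tempting to conclude that remote adherence will be under-scored. That follows only on the literal reading with a lag above zero, and only if waiting days are left in at analysis. The plan settles none of these.

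The point concerns Secondary Objective 2 and the fidelity of the OTC simulation. It does not by itself bias the primary between-arm comparison or affect the sample size.

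**What to change.** - Reconcile Behavioral Support with Appendix 10 by removing the restated instruction from the Week 2 item.
- Record the date of the first study pill. Then ask on how many days since that date the participant took no pills, one pill or two pills.
- State in the SAP that days 1–3 and day 4 onward are scored against the assigned schedule at analysis, without the schedule being read to the participant.
- For remote data already collected, use the start date reported to staff to identify pre-medication days. In both cohorts, flag Week 2 answers obtained with the present wording.
- The Week 4, 8 and 12 items do not restate the instruction and need no change on that ground.

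The cost is one reworded form item, one date field and a short scoring rule. No visits or additional participant contacts are added.
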